#### **14.6 Incidental or Unexpected Findings:**

Describe the plan to address incidental findings and unexpected findings about individuals from screening to the end of the subject's participation in the research. In cases where the subject could possibly benefit medically or otherwise from the information, state whether or not the results of screening, research participation, research tests, etc., will be shared with subjects or their primary care provider. State whether the researcher is obligated or mandated to report results to appropriate military or civilian authorities and explain the potential impact on the subject

Due to the study design, incidental or unexpected findings are highly unlikely. Ketorolac is an NSAID which has held FDA approval since May 16, 1997. The study is designed to compare two doses of ketorolac which are very commonly used to treat pain in EDs and in other areas of medicine nationwide.

However, any incidental or unexpected findings will be discussed with the patient and the attending provider. If permission is granted from the attending provider and patient in written form (through the use of a medical disclosure form) and shared with the appropriate WBAMC authorities and the DCI. However, again, these findings are highly unlikely for this study and with the use of such a well understood medication such as ketorolac.

## 15.0 Study Monitoring

### 15.1 Your study requires either Data and Safety Monitoring Plan (DSMP) or a Data and Safety Monitoring Board (DSMB).

- DSMP
- DSMB
- Both
- Not Applicable

## 16.0 Reportable Events

### 16.1 Reportable Events: Consult with the research office at your institution to ensure requirements are met. Describe plans for reporting unexpected adverse events and unanticipated problems. Address how unexpected adverse events will be identified, who will report, how often adverse events and unanticipated problems will be reviewed to determine if any changes to the protocol or consent form are needed and the scale that will be used to grade the severity of the adverse event.

Consult with the research office at your institution to ensure requirements are met

- Describe plans for reporting expected adverse events. Identify what the expected adverse events will be for this study, describe the likelihood (frequency, severity, reversibility, short-term management and any long-term implications of each expected event)
- Describe plans for reporting unexpected adverse events and unanticipated problems. Address how unexpected adverse events will be identified, who will report, how often adverse events and unanticipated problems will be reviewed to determine if any changes to the research protocol or consent form are needed and the scale that will be used to grade the severity of the adverse event

All unanticipated problems involving risk to subjects or others, unexpected serious adverse events, and all subject deaths related or possibly related to the study will be reported promptly providing initial notification of the event as quickly as possible after the research team's knowledge of the event, but within five (5) business days of identification by [contact]), by e-mail ([contact]), by [contact]) or via letter addressed to IRB Administrator, Regional Health Command-Central Office of the Institutional Review Board, Brooke Army Medical Center, Attn: MCHE-ZQ, Department of Quality and Safety, [name]. A complete written report will follow the initial notification within 10 working days.

Reportable events may include any serious adverse event directly related to the administration of intramuscular ketorolac during the conduct of this study; such as hospitalization, GI bleed, anaphylaxis, infection at the injection site, death, or other unexpected adverse event which requires additional treatment.

Any expected adverse events (i.e. risks outlined in section 14.1 of this protocol) will be documented in the adverse events log and submitted to the IRB at the time of continuing review.

The study team will consult with the William Beaumont Human Research Protections Office for assistance in submitting any reportable events.

## 17.0 Equipment/non-FDA Regulated Devices

### 17.1 Does the study involve the use of any unique non-medical devices/equipment?

Yes  No

## 18.0 FDA-Regulated Products

### 18.1 Will any drugs, dietary supplements, biologics, or devices be utilized in this study?

- Drugs
- Dietary Supplements
- Biologics
- Devices
- N/A

### 18.2 Drugs, Dietary Supplements and Biologics/Vaccines details:

- Are drug(s) in this research being used in accordance to the approved labeling?
- Are drug(s) in this research being used in a manner other than its approved labeling?

Enter Dietary Supplements and Biologics/Vaccines in the Drug Information table. Complete all relevant fields in the table ("Protocol Drug Details" screen). If the question is not relevant, leave the question blank and/or do not change the default selection.

View Details	Drug Name	FDA Approved	A new drug or a new use of approved drug:	IND Number
⊖	Trade Drug Name: KETOROLAC Generic Drug Name: Investigational Drug Name:	Yes	No	

Trade Drug Name:	KETOROLAC
Generic Drug Name:	
Investigational Drug Name:	
Identify the name of the manufacturer or source of investigational drug/biologic:	Roche
Is the drug supplied at no cost?	Yes
Is the Drug FDA Approved:	

Is this a new drug or a new use of an already approved drug	No
Is an IND necessary	No
IND Number	
Who holds the IND:	N/A
IND details:	
If FDA Approved and an IND is not required, Please provide a rationale for exemption:	N/A
Are you currently using this IND in another research project?	No
If yes, list the IRB Number(s):	
Dose Range:	15mg-60mg
Frequency:	Once
Route of administration:	IM
Will the investigational pharmacy be dispensing?	No
If the source is not a FDA licensed facility, provide details regarding the purity, quality, stability and sterility of the investigational drug/biologic:	N/A
Identify who will be preparing the investigational drug/biologic for administration and describe in detail how it will be prepared:	Emergency Department nursing staff caring for the subjects will prepare drug for administration.
Indication(s) under Investigation:	Acute Musculoskeletal Pain
Where will the drug be stored	Within the Emergency Department medication omnicell.
Drug Storage Restrictions (including temperature, etc.):	The medication is stored in accordance with William Beaumont Pharmacy policies.
Administration Instructions:	The medication should be administered slowly and deeply into the muscle, in accordance with product labeling.
Possible Untoward Effects, Their Symptoms & Treatment:	Nausea, vomiting, abdominal pain, drowsiness, and lethargy, Patients should be managed by symptomatic and supportive care following overdose
Potential or Actual Antidotes for Excessive or Adverse Drug Effect:	N/A
	
Ketorolac Tromethamine is contraindicated in patients with previously demonstrated hypersensitivity to ketorolac.
 
Warnings include The total combined duration of use of oral ketorolac tromethamine and IV or IM dosing of ketorolac tromethamine is not to exceed 5 days in adults. Ketorolac tromethamine is not indicated for use in pediatric patients.
 
The most serious risks associated with ketorolac tromethamine are:
 
Gastrointestinal Effects- Risk of Ulceration, Bleeding, and Perforation
 
Ketorolac tromethamine is contraindicated in patients with previously documented peptic ulcers and/or GI bleeding.
 
Ketorolac tromethamine can cause serious gastrointestinal (GI) adverse events including bleeding, ulceration and perforation, of the stomach, small intestine, or large intestine, which can be fatal. These serious adverse events can occur at any time, with or without warning symptoms, in patients treated with ketorolac tromethamine.

Only one in five patients who develop a serious upper GI adverse event on NSAID therapy is symptomatic. Minor upper gastrointestinal problems, such as dyspepsia, are common and may also occur at any time during NSAID therapy. The incidence and severity of gastrointestinal complications increases with increasing dose of, and duration of treatment with, ketorolac tromethamine. Do not use ketorolac tromethamine for more than five days.

However, even short-term therapy is not without risk. In addition to past history of ulcer disease, other factors that increase the risk for GI bleeding in patients treated with NSAIDs include concomitant use of oral corticosteroids, or anticoagulants, longer duration of NSAID therapy, smoking, use of alcohol, older age, and poor general health status. Most spontaneous reports of fatal GI events are in elderly or debilitated patients and therefore, special care should be taken in treating this population.

To minimize the potential risk for an adverse GI event, the lowest effective dose should be used for the shortest possible duration. Patients and physicians should remain alert for signs and symptoms of GI ulceration and bleeding during NSAID therapy and promptly initiate additional evaluation and treatment if a serious GI adverse event is suspected. This should include discontinuation of ketorolac tromethamine until a serious GI adverse event is ruled out. For high risk patients, alternate therapies that do not involve NSAIDs should be considered.

NSAIDs should be given with care to patients with a history of inflammatory bowel disease (ulcerative colitis, Crohn's disease) as their condition may be exacerbated.

#### Hemorrhage

Because prostaglandins play an important role in hemostasis and NSAIDs affect platelet aggregation as well, use of ketorolac tromethamine in patients who have coagulation disorders should be undertaken very cautiously, and those patients should be carefully monitored. Patients on therapeutic doses of anticoagulants (e.g., heparin or dicumarol derivatives) have an increased risk of bleeding complications if given ketorolac tromethamine concurrently; therefore, physicians should administer such concomitant therapy only extremely cautiously. The concurrent use of ketorolac tromethamine and therapy that affects hemostasis, including prophylactic low-dose heparin (2500 to 5000 units q12h), warfarin and dextrans have not been studied extensively, but may also be associated with an increased risk of bleeding. Until data from such studies are available, physicians should carefully weigh the benefits against the risks and use such concomitant therapy in these patients only extremely cautiously.

Patients receiving therapy that affects hemostasis should be monitored closely.

In postmarketing experience, postoperative hematomas and other signs of wound bleeding have been reported in association with the peri-operative use of IV or IM dosing of ketorolac tromethamine. Therefore, peri-operative use of ketorolac tromethamine should be avoided and postoperative use be undertaken with caution when hemostasis is critical (see PRECAUTIONS).

#### Renal Effects

Long-term administration of NSAIDs has resulted in renal papillary necrosis and other renal injury. Renal toxicity has also been seen in patients in whom renal prostaglandins have a compensatory role in the maintenance of renal perfusion. In these patients, administration of a NSAID may cause a dose-dependent reduction in prostaglandin formation and, secondarily, in renal blood flow, which may precipitate overt renal decompensation. Patients at greatest risk of this reaction are those with impaired renal function, heart failure, liver dysfunction, those taking diuretics and ACE inhibitors, and the elderly. Discontinuation of

NSAID therapy is usually followed by recovery to the pretreatment state. Ketorolac tromethamine and its metabolites are eliminated primarily by the kidneys, which, in patients with reduced creatinine clearance, will result in diminished clearance of the drug (see CLINICAL PHARMACOLOGY). Therefore, ketorolac tromethamine should be used with caution in patients with impaired renal function (see DOSAGE AND ADMINISTRATION) and such patients should be followed closely. With the use of ketorolac tromethamine, there have been reports of acute renal failure, interstitial nephritis and nephrotic syndrome.

**Impaired Renal Function**

Ketorolac tromethamine is contraindicated in patients with serum creatinine concentrations indicating advanced renal impairment (see CONTRAINDICATIONS). Ketorolac tromethamine should be used with caution in patients with impaired renal function or a history of kidney disease because it is a potent inhibitor of prostaglandin synthesis. Because patients with underlying renal insufficiency are at increased risk of developing acute renal decompensation or failure, the risks and benefits should be assessed prior to giving ketorolac tromethamine to these patients.

Interactions include Ketorolac is highly bound to human plasma protein (mean 99.2%). There is no evidence in animal or human studies that ketorolac tromethamine induces or inhibits hepatic enzymes capable of metabolizing itself or other drugs.

**Warfarin, Digoxin, Salicylate, and Heparin:** The in vitro binding of warfarin to plasma proteins is only slightly reduced by ketorolac tromethamine (99.5% control vs 99.3%) when ketorolac plasma concentrations reach 5 to 10 mcg/mL. Ketorolac does not alter digoxin protein binding. In vitro studies indicate that, at therapeutic concentrations of salicylate (300 mcg/mL), the binding of ketorolac was reduced from approximately 99.2% to 97.5%, representing a potential twofold increase in unbound ketorolac plasma levels. Therapeutic concentrations of digoxin, warfarin, ibuprofen, naproxen, piroxicam, acetaminophen, phenytoin and tolbutamide did not alter ketorolac tromethamine protein binding.

In a study involving 12 adult volunteers, oral ketorolac tromethamine was coadministered with a single dose of 25 mg warfarin, causing no significant changes in pharmacokinetics or pharmacodynamics of warfarin. In another study, ketorolac tromethamine dosed IV or IM was given with two doses of 5000 U of heparin to 11 healthy volunteers, resulting in a mean template bleeding time of 6.4 minutes (3.2 to 11.4 min) compared to a mean of 6 minutes (3.4 to 7.5 min) for heparin alone and 5.1 minutes (3.5 to 8.5 min) for placebo. Although these results do not indicate a significant interaction between ketorolac tromethamine and warfarin or heparin, the administration of ketorolac tromethamine to patients taking anticoagulants should be done extremely cautiously, and patients should be closely monitored (see WARNINGS and PRECAUTIONS: Hematologic Effect).

The effects of warfarin and NSAIDs, in general, on GI bleeding are synergistic, such that the users of both drugs together have a risk of serious GI bleeding higher than the users of either drug alone.

**Aspirin:** When ketorolac tromethamine is administered with aspirin, its protein binding is reduced, although the clearance of free ketorolac tromethamine is not altered. The clinical significance of this interaction is not known; however, as with other NSAIDs, concomitant administration of ketorolac tromethamine and aspirin is not generally recommended because of the potential of increased adverse effects.

**Diuretics:** Clinical studies, as well as postmarketing observations,

#### Contraindications and Interactions, If Known:

have shown that ketorolac tromethamine can reduce the natriuretic effect of furosemide and thiazides in some patients. This response has been attributed to inhibition of renal prostaglandin synthesis. During concomitant therapy with NSAIDs, the patient should be observed closely for signs of renal failure (see **WARNINGS: Renal Effects**), as well as to assure diuretic efficacy.

**Probenecid:** Concomitant administration of oral ketorolac tromethamine and probenecid resulted in decreased clearance and volume of distribution of ketorolac and significant increases in ketorolac plasma levels (total AUC increased approximately threefold from 5.4 to 17.8 mcg/h/mL) and terminal half-life increased approximately twofold from 6.6 to 15.1 hours. Therefore, concomitant use of ketorolac tromethamine and probenecid is contraindicated.

**Lithium:** NSAIDs have produced an elevation of plasma lithium levels and a reduction in renal lithium clearance. The mean minimum lithium concentration increased 15% and the renal clearance was decreased by approximately 20%. These effects have been attributed to inhibition of renal prostaglandin synthesis by the NSAID. Thus, when NSAIDs and lithium are administered concurrently, subjects should be observed carefully for signs of lithium toxicity.

**Methotrexate:** NSAIDs have been reported to competitively inhibit methotrexate accumulation in rabbit kidney slices. This may indicate that they could enhance the toxicity of methotrexate. Caution should be used when NSAIDs are administered concomitantly with methotrexate.

**ACE Inhibitors/Angiotensin II Receptor Antagonists:** Concomitant use of ACE inhibitors and/or angiotensin II receptor antagonists may increase the risk of renal impairment, particularly in volume-depleted patients.

Reports suggest that NSAIDs may diminish the antihypertensive effect of ACE inhibitors and/or angiotensin II receptor antagonists. This interaction should be given consideration in patients taking NSAIDs concomitantly with ACE inhibitors and/or angiotensin II receptor antagonists.

**Antiepileptic Drugs:** Sporadic cases of seizures have been reported during concomitant use of ketorolac tromethamine and antiepileptic drugs (phenytoin, carbamazepine).

**Psychoactive Drugs:** Hallucinations have been reported when ketorolac tromethamine was used in patients taking psychoactive drugs (fluoxetine, thiothixene, alprazolam).

**Pentoxifylline:** When ketorolac tromethamine is administered concurrently with pentoxifylline, there is an increased tendency to bleeding.

**Nondepolarizing Muscle Relaxants:** In postmarketing experience there have been reports of a possible interaction between ketorolac tromethamine IV/IM and nondepolarizing muscle relaxants that resulted in apnea. The concurrent use of ketorolac tromethamine with muscle relaxants has not been formally studied.

**Selective Serotonin Reuptake Inhibitors (SSRIs):** There is an increased risk of gastrointestinal bleeding when selective serotonin reuptake inhibitors (SSRIs) are combined with NSAIDs. Caution should be used when NSAIDs are administered concomitantly with SSRIs.

**Carcinogenesis, Mutagenesis and Impairment of Fertility**  
An 18-month study in mice with oral doses of ketorolac tromethamine at 2 mg/kg/day (0.9 times the human systemic exposure at the recommended IM or IV dose of 30 mg qid, based on area-under-the-plasma-concentration curve [AUC]), and a 24-month study in rats at 5 mg/kg/day (0.5 times the human AUC) showed no evidence of tumorigenicity.

Ketorolac tromethamine was not mutagenic in the Ames test, unscheduled DNA synthesis and repair, and in forward mutation assays. Ketorolac tromethamine did not cause chromosome breakage in the in vivo mouse micronucleus assay. At 1590 mcg/mL and at higher

	
concentrations, ketorolac tromethamine increased the incidence of chromosomal aberrations in Chinese hamster ovarian cells. Impairment of fertility did not occur in male or female rats at oral doses of 9 mg/kg (0.9 times the human AUC) and 16 mg/kg (1.6 times the human AUC) of ketorolac tromethamine, respectively.
 
Ketorolac tromethamine is contraindicated in patients with active peptic ulcer disease, in patients with recent gastrointestinal bleeding or perforation and in patients with a history of peptic ulcer disease or gastrointestinal bleeding.
 
Ketorolac tromethamine should not be given to patients who have experienced asthma, urticaria, or allergic-type reactions after taking aspirin or other NSAIDs. Severe, rarely fatal, anaphylactic-like reactions to NSAIDs have been reported in such patients (see WARNINGS – Anaphylactoid Reactions, and PRECAUTIONS – Preexisting Asthma).
 
Ketorolac tromethamine is contraindicated as prophylactic analgesic before any major surgery.
 
Ketorolac tromethamine is contraindicated for the treatment of peri-operative pain in the setting of coronary artery bypass graft (CABG) surgery (see WARNINGS).
 
Ketorolac tromethamine is contraindicated in patients with advanced renal impairment or in patients at risk for renal failure due to volume depletion (see WARNINGS for correction of volume depletion).
 
Ketorolac tromethamine is contraindicated in labor and delivery because, through its prostaglandin synthesis inhibitory effect, it may adversely affect fetal circulation and inhibit uterine musculature, thus increasing the risk of uterine hemorrhage.
 
The use of ketorolac tromethamine is contraindicated in nursing mothers because of the potential adverse effects of prostaglandin-inhibiting drugs on neonates.
 
Ketorolac tromethamine inhibits platelet function and is, therefore, contraindicated in patients with suspected or confirmed cerebrovascular bleeding, hemorrhagic diathesis, incomplete hemostasis and those at high risk of bleeding (see WARNINGS and PRECAUTIONS).
 
Ketorolac tromethamine is contraindicated in patients currently receiving aspirin or NSAIDs because of the cumulative risks of inducing serious NSAID-related adverse events.
 
The concomitant use of ketorolac tromethamine and probenecid is contraindicated.
 
The concomitant use of ketorolac tromethamine and pentoxifylline is contraindicated.
 
Ketorolac tromethamine injection is contraindicated for neuraxial (epidural or intrathecal) administration due to its alcohol content.

#### 18.4 Reporting Requirements for FDA-regulated research under IND and IDE:

Describe the process for complying with FDA regulatory requirements for adverse event reporting and adverse device effects reporting to the sponsor

N/A

#### 18.5 Sponsor (organization/institution/company):

N/A

If applicable, provide sponsor contact information:

---

## 19.0

### Research Registration Requirements

#### 19.1 ClinicalTrials.gov Registration:

- Registration is not required
- Registration pending
- Registration complete

#### 19.2 Defense Technical Information Center Registration (Optional):

- Registration is not required
- Registration pending
- Registration complete

## 20.2 Abbreviations and Acronyms:

Cyclooxygenase-1 (COX-1)  
Cyclooxygenase-2 (COX-2)  
Department of Defense (DoD)  
Department of Veterans Affairs (VA)  
Electronic Health Record (EHR)  
Emergency Department (ED)  
Emergency Severity Index (ESI)  
Food and Drug Administration (FDA)  
Health Insurance Portability and Accountability Act (HIPAA)  
Human-Chorionic Gonadotropin (HCG)  
Intramuscular (IM)  
Intravenous (IV)  
Medical Record Number (MRN)  
Milligram (mg)  
Milliliter (mL)  
Millimeter (mm)  
Millimeters of Mercury (mmHg)  
Minimum Clinical Significant Difference (MCSD)  
Nonsteroidal anti-inflammatory drug (NSAID)  
Primary Investigator (PI)  
Protected Health Information (PHI)  
Personally Identifiable Information (PII)  
Visual Analog Scale (VAS)

Cover Page

Title: Comparison of Intramuscular Ketorolac at Two Single-Dose Regimens for Treatment of Acute Musculoskeletal Pain in a Military Emergency Department: A Randomized Controlled Non-Inferiority Trial

NCT: Not received yet

Date: 2/5/2021

Statistical Analysis Plan

Data analysis will be performed using the statistical software SPSS (IBM SPSS Statistics for Windows, Version 26.0. Armonk, NY: IBM Corp.). The primary outcome will be tested using an independent samples *t*-test. To assess for any differences in VAS scores based on demographic data, independent *t*-tests will be utilized. To assess for normality of distributions in the sample's continuous demographic and clinical characteristics, z-scores will be formed by dividing skewness by the standard error of skewness. This is performed to ensure that parametric measures can be used for the two groups. A Fisher's exact test will be used to assess the lower dose for a difference in adverse effects. During analysis, it was determined that the pain reduction variables could be compared by age and body weight using Pearson correlations. Additionally, the pain reduction variables will be compared by gender, duration of pain (\leq 24 hours vs. $>$ 24 hours), and location of pain (back/neck vs. other locations and small vs. large joints) using independent *t*-tests.

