#### 9.3

##### **Objectives/Specific Aims/Research Questions:**

Describe the purpose and objective(s) of the study, specific aims, and/or research questions/hypotheses

**Purpose:** The purpose of this study is to evaluate the effectiveness of 15 mg ketorolac versus 60 mg ketorolac injected intramuscularly for the treatment of acute musculoskeletal pain in military emergency department patients.

The alternative hypothesis is that 15 mg intramuscular ketorolac will be non-inferior when compared to 60 mg intramuscular ketorolac for the treatment of acute musculoskeletal pain in military emergency department patients.

The null hypothesis is that 15 mg intramuscular ketorolac will be inferior when compared to 60 mg intramuscular ketorolac for the treatment of acute musculoskeletal pain in military emergency department patients.

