### **Primary Outcome Variable Data:**

The primary outcomes will be a clinically significant reduction in the numeric rating using the visual analog scale at 30 and 60 minutes from medication administration and compared to the pre-treatment VAS.

The primary outcome variables will be the change in subjective pain reported by patients using a VAS. The VAS is a validated measurement instrument used to record subjective reports of pain, or other subjective conditions. There are several different VAS constructs but this study will utilize a single horizontal line measuring 0-100 mm with short vertical marks as borders at each edge. All investigators will independently measure the VAS line to ensure that the printed line on the VAS form measures exactly 100 mm. The phrase "No pain" will be placed to the left of the 0 mm mark and the phrase "Severe Pain" will be placed to the right of the 100 mm mark. There will be no numerical or other incremental marks along, within or above the scale. The study subject will be instructed on the use of the scale prior to having their pain assessed. They will be informed that the scale measures from left to right, least to greatest level of pain. To annotate their pain level, they will be instructed to signify their level of pain on a scale of "0 mm or no pain at all" to "100 mm or Severe Pain" by making a single vertical mark through the horizontal VAS line on the document. If they do not make a vertical mark (circle, forward slash, backward slash, or otherwise), it is not through the horizontal VAS line, or illegible the investigator will retrain the patient on how to complete the form and a new form will be provided for the patient. An extra VAS is included in each Subject Study Packet for this purpose. Once completed, the forms will be returned to the subject study packet.

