### **11.0 Statistical/Data Analysis Plan**

#### **11.1 Statistical Considerations:**

List the statistical methods to be used to address the primary and secondary objectives, specific aims, and/or research hypotheses. Explain how missing data and outliers will be handled in the analysis. The analysis plan should be consistent with the study objectives. Include any sub-group analyses (e.g., gender or age group). Specify statistical methods and variables for each analysis. Describe how confounding variables will be controlled in the data analysis

The primary outcome will be the difference in VAS from baseline to 30 minutes and from baseline to 60 minutes. Our research hypothesis is that the measured pain relief using 15mg of intramuscular ketorolac will be non-inferior to the measured pain relief using 60mg of intramuscular ketorolac. Whereas in a clinical study where the research hypothesis is that one treatment, say drug A, is demonstrated to have a better (improved pain relief) outcome than the second treatment, say drug B, we are hypothesizing that smaller dose drug is not inferior in terms of pain relief than the higher drug dose. We fully suspect that the higher drug dose will have a better average outcome, but the question of interest is, is the outcome for the lower dose drug non-inferior to that of the higher drug dose. The analysis used in this study is a non-inferiority test. This hypothesis can be tested using a variety of methods that involve the construction of one-sided confidence interval or one-sided, two-sample equal-variance t-test with alpha of 0.05. In both methods, the power and sample size can be computed.

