**11.5 Please provide a justification for your sample size**

In this study, we assume that we are comparing the mean VAS between the 2 Groups, and the margin of non-inferiority is -13 mm. The actual difference between the means is assumed to be 0 and the standard deviation is assumed to be 27 for the 2 Groups (estimated from the Motov manuscript). Group sample sizes of 55 and 55 achieve 80% power to detect non-inferiority using a one-sided, two-sample equal-variance t-test with alpha of 0.05. The sample size per arm was increased from 55 to 61 to account for an anticipated 10% dropout or withdrawal of subjects (5.5 subjects was rounded to 6 subjects).

**11.6 Data Analysis Plan: Complete description: Background, Objectives, Design, Step by Step how the project is going to be done, Data analysis plan:**

To test for non-inferiority of dose 15mg to dose 60 mg using the VAS pain score, the analysis to be used is called an interval test. The hypothesis will be tested using the construction of one-sided confidence intervals or one-sided, two-sample equal-variance t-test with alpha of 0.05. To test that the lower dose has less adverse effects, we will use the one-sided z-test for testing two independent proportions. All tests will be conducted at the 0.05 level of significance.

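### The SAP gives the primary analysis only as an independent-samples t-test and does not carry over the protocol's non-inferiority rule (one-sided 0.05, margin -13 mm)

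*SAP*

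**What the plan says.** **Protocol.** Section 9.3 sets the hypotheses: "The alternative hypothesis is that 15 mg intramuscular ketorolac will be non-inferior when compared to 60 mg intramuscular ketorolac"; the null is that 15 mg is inferior. Section 11.1 says "The analysis used in this study is a non-inferiority test", and adds both an expectation, "We fully suspect that the higher drug dose will have a better average outcome", and a purpose: "the question of interest is, is the outcome for the lower dose drug non-inferior to that of the higher drug dose". The same section fixes the outcome: "The primary outcome will be the difference in VAS from baseline to 30 minutes and from baseline to 60 minutes". Section 10.2 names the same two times.

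Section 11.5 states that "the margin of non-inferiority is -13 mm" and bases the sample size on a one-sided 0.05 equal-variance two-sample t-test. Section 11.6 repeats that test, or a one-sided confidence interval, as the analysis. Section 10.2 also takes 13 mm as the minimum clinically significant change in VAS and sends the reader to the statistical section.

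**SAP (one paragraph, dated 2/5/2021).** The primary analysis has one sentence: "The primary outcome will be tested using an independent samples" *t*-test. The only mention of non-inferiority is in the trial title. There is no margin, null, sidedness, alpha, confidence bound or pointer to the protocol.

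**The concern.** A t-test named without a null is ordinarily a test of zero difference. The SAP paragraph uses the same unqualified wording for its comparisons by gender, pain duration and pain location, which look for ordinary differences. Nothing marks the primary t-test as a different kind of test.

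A test of zero difference cannot establish non-inferiority, because failing to find a difference does not rule out a deficit of 13 mm. It also answers a question the protocol does not ask: section 11.1 expects 60 mg to do better on average and wants to know only whether 15 mg is non-inferior.

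The stated 80% power and 0.05 error level belong to the margin-based test. Anyone working from the SAP alone has no rule for making the trial's central claim.

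**Working it through.** **Inputs, all from protocol section 11.5:** margin 13 mm, SD 27 mm in each arm, true difference 0, one-sided alpha 0.05, power 80%, 55 evaluable per arm, 61 per arm enrolled.

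**1. Reproduce the plan's sample size.** By the normal approximation, n per arm = 2 × (1.645 + 0.842)² × 27² / 13² = 53.3, so 54. With the exact noncentral t distribution, 54 per arm falls just short of 80% (79.98%) and 55 per arm gives 80.6%. The stated 55 is therefore right for the margin-based test; 61 per arm gives 84.1%. The design rests on the test that the SAP leaves out.

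**2. Standard error of the difference,** 27 × √(2/n):
- 55 per arm: 5.149 mm (108 df)
- 61 per arm: 4.889 mm (120 df)

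**3. Largest observed shortfall of 15 mg that meets the margin,** 13 − t(0.95) × SE:
- 55 per arm: 13 − 1.659 × 5.149 = 4.5 mm
- 61 per arm: 13 − 1.658 × 4.889 = 4.9 mm

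**4. Largest observed shortfall that is non-significant against zero,** t(0.975) × SE. This assumes a two-sided 0.05 test, which the SAP does not state:
- 55 per arm: 1.982 × 5.149 = 10.2 mm
- 61 per arm: 1.980 × 4.889 = 9.7 mm

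Shortfalls between the limits in steps 3 and 4 are non-significant yet fail the margin. For example, an observed shortfall of 7 mm at 61 per arm gives t = 7/4.889 = 1.43, below 1.980. Its lower one-sided 95% bound is −7 − 1.658 × 4.889 = −15.1 mm, which is beyond −13. At SD 27 the misreading errs in one direction only, since any shortfall small enough to meet the margin is also non-significant.

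**5. How often a true 13 mm deficit would pass,** if non-significance in step 4 were read as non-inferiority (a second assumption that neither document states). The noncentrality is 13/SE.

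| | 55 per arm | 61 per arm |
|---|---|---|
| Noncentrality | 13/5.149 = 2.52 | 13/4.889 = 2.66 |
| P(non-significant against zero) | 0.294 | 0.249 |
| P(margin rule met) | 0.05 | 0.05 |

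A simulation of 400,000 trials agrees: 0.292 and 0.249 for the test against zero, 0.049 and 0.050 for the margin rule.

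**6. Can the SAP be assumed to inherit the protocol's rule?** For the primary outcome both documents name a two-sample t-test, so nothing conflicts. For adverse effects, protocol 11.6 plans a one-sided z-test for two proportions, while the SAP names Fisher's exact test. The SAP therefore departs from the protocol at least once, and neither document says which governs.

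**The case against.** The strongest reply is that the plan, read as a whole, already has the rule. Section 9.3 gives the null, 11.1 the time points, and 11.5 and 11.6 the margin, sidedness and alpha; section 10.2 attaches clinical meaning to 13 mm. The SAP's test is of the same family, and its reference to the primary outcome picks up the definition in 11.1. The change to Fisher's exact test concerns a secondary outcome and is stated openly. It fits equally well with a SAP that names what it changes and leaves the rest alone.

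Much of this stands. The missing elements are absent from the SAP, not from the plan, and the SAP's silence on time points is answered by 11.1. What remains is that the SAP neither restates nor cites the rule. Nor does the protocol write it out as a single criterion: the margin is in 11.5, the test is in 11.6, and the reader must join them.

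Two stronger readings are tempting. A reader might infer that the SAP has abandoned non-inferiority for a superiority-type test. No sentence in it says so, and the title still calls this a non-inferiority trial. A reader might also take 29% or 25% as the trial's planned error rate. Those figures need a two-sided test against zero and a reading of non-significance as non-inferiority. The SAP states neither, and the second runs against the protocol's null of inferiority.

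**Conclusion.** The point holds as an omission: the SAP fails to carry over the protocol's non-inferiority test, and its sentence, followed literally, gives a test that cannot support the trial's conclusion. It is not shown to be an override or a contradiction.

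The size of the possible harm is conditional on SD 27 and the two assumptions in the working. On those terms a true 13 mm deficit would pass about 29% of the time with 55 per arm, or 25% with 61, instead of 5%. The 5% applies to each time point separately; the documents do not say how 30 and 60 minutes combine, so no trial-level rate is established. Confidence is high on the omission and lower on the consequence, which depends on how the test would be run and read. Severity: should-fix.

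**What to change.** Replace the SAP's sentence on the primary outcome with:

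> The primary outcome is the change in VAS from baseline to 30 and to 60 minutes (protocol 11.1). At each time point the difference in mean reduction (15 mg minus 60 mg) will be tested with the one-sided, equal-variance two-sample t-test at alpha 0.05 against the -13 mm margin (protocol 11.1, 11.5, 11.6). Non-inferiority is concluded only if the lower one-sided 95% confidence bound is above -13 mm. A non-significant test of zero difference will not be read as non-inferiority.

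Date the change. The margin, alpha and equal-variance test are the protocol's own. Change from baseline follows 11.1 (11.5 speaks only of mean VAS), and the direction of subtraction makes explicit what the negative margin implies. The cost is one sentence and no new data: the bound is the lower limit of the two-sided 90% interval from the same t-test.

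Separately, state whether the overall claim requires both time points to pass. Protocol 10.2 and 11.1 name both but do not settle this, so it is a new decision and not part of the restored rule. Date it and label it as new. The SAP describes its age and body-weight comparisons as decided in the course of analysis, so analysis may already have begun and the choice may be post hoc.
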